3. RATIONALE FOR THE STUDY

Mexico has one of the highest prevalence of obesity worldwide. According to data from ENSANUT 2012, 32.4% of people older than 20 years have obesity, which means that 22 millions of Mexicans have this pathology. This survey described that 1.8% of male and 4.1% of female population have obesity class III. This disease is characterized by an increased risk of comorbidities as T2D, atherogenic dyslipidemia, HTN, obstructive sleep apnea hypopnea syndrome, as well as an increase in proinflammatory cytokines from adipose tissue, which results in a decrease in life expectancy in the economically active population, increased mortality and high costs for the healthy system derived from direct or indirect attention.

Since 2008 in the Hospital de Especialidades Centro Médico Nacional Siglo XXI, the Endocrinology Department organized an Obesity Clinic with the purpose of generating learning strategies of changes in lifestyle, control of comorbidities related with obesity and achieve the weight decrease of patients with obesity class III needed to undergo for bariatric surgery. However, many patients fail to meet weight reduction despite reporting good adherence to diet and exercise strategies. Despite pharmacological treatment is required in these patients, the deleterious cardiovascular effects of current treatments contraindicate its use in this population.

At this point, new pharmacological strategies focused on people with obesity class III are required. Those strategies need to help in weight decrease and should induce benefits on other cardiometabolic parameters such as HTN, increased glucose concentration, hypertriglyceridemia, decreased HDL-c and abdominal obesity.

4. JUSTIFICATION FOR THE STUDY

Recently, it has been approved for the treatment of T2D, a group of drugs known as inhibitors of sodium-glucose co-transporter type 2 (iSGLT2) whose main mechanism of action is the induction of glycosuria. Dapagliflozin was the first marketed drug in this class and has a large number of studies that have demonstrated its effect on glucose lowering with good safety profile and tolerability. Furthermore, it has been observed that induces weight loss and also decrease in blood pressure, triglycerides, waist circumference by loss of fat mass and increased HDL-c and adiponectin concentrations. These effects have been evaluated in patients with T2D with normal BMI, overweight and obesity grade I and II but have not been evaluated in patients with class III obesity or higher. Furthermore, there is a lack of information about its effects on inflammatory cytokine concentrations (resistin, IL-6, IL-10 and TNF- α) or in the glucagon concentration.

Based on previous studies (not yet published), up to 46% of patients at Obesity Clinic have prediabetes or diabetes. The use of dapagliflozin in this population could increase weight loss and improve other cardiovascular factors. This could be translated into decreased time needed to undergo surgical treatment and better control of associated comorbidities.

RESEARCH QUESTION

What is the efficacy of dapagliflozin and metformin combination in comparison with monotherapy with metformin for decrease on weight, waist circumference, triacylglycerol, blood pressure and inflammatory cytokines in patients with prediabetes or diabetes and obesity class III?

5. HYPOTHESIS

Dapagliflozin in combination with metformin induce 10% of weight lost and 5% of decrease in waist circumference, triacylglycerol concentration, blood pressure and inflammatory cytokines in patients with prediabetes or diabetes with class III obesity, in comparison with the 5% of weight lost and lack of effect in the rest of parameters in patients treated with metformin monotherapy.

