6. OBJECTIVES

- a. **Primary objective:** To determine if combined treatment with dapagliflozin and metformin is more effective than monotherapy with metformin for weight loss and assess its effects on waist circumference, triglycerides, blood pressure and inflammatory cytokines in patients with prediabetes and diabetes with obesity class III.
- b. **Secondary objectives:**
 - i. To determine efficacy of metformin monotherapy for weight loss and decrease on waist circumference, triglycerides and blood pressure in patients with prediabetes and diabetes with obesity class III.
 - ii. To compare efficacy of metformin monotherapy and combined treatment with metformin and dapagliflozin.
 - iii. To determine the percentage of patients that with combined treatment achieves a decrease in total weight of 5%, 10% and 15% and the percentage of patients that achieve a decrease in 10% of excess weight.
 - iv. To evaluate if combined treatment allows a decrease in number of drugs needed for comorbidities' control.
 - v. To evaluate prevalence of adverse effects commonly associated with dapagliflozin use (urinary and genital tract infections, hydroelectrolytic alterations) in patients with obesity class III.
 - vi. To determine serum concentration of adiponectin, resistin, IL-6, IL-10 and TNF- α before and after treatments, and compare it between groups.
 - viii. To determine serum concentration of insulin, glucagon and ghrelin before and after treatments, and compare it between groups.

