6. Use of drugs for weight control.
7. Untreated or uncontrolled hypothyroidism (defined through TSH higher than 4.2 μ U/ml)
8. Pregnant or lactating mother.
9. Tobacco use (in the last month)
10. Current use of steroids or nonsteroidal anti-inflammatory drugs

Withdrawal criteria

1. Becoming pregnant during the study
2. Tobacco use
3. Use of steroids during the study

Sample size

Weight loss after dapagliflozin treatment has not been previously used as primary outcome in randomized controlled trials (RCT) of patients with prediabetes or diabetes and grade III obesity. Zhang et al. performed a meta-analysis that included seven RCTs evaluating the effect of metformin combined with SGLT2-inhibitors (dapagliflozin 10 mg/day, canagliflozin 300 mg/day, empagliflozin 25 mg/day, or ipragliflozin 300 mg/day) vs. metformin (at doses of 1.5 to 3 g/day) with placebo on HbA1c; fasting plasma glucose; and body weight over 24 weeks, 1 year, and 2 years. The total sample was 2847 patients with a mean BMI of 31.7 ± 4.9 kg/m². After a year of treatment, the placebo-metformin control group showed a reduction in body weight of 1.1 ± 3.39 kg, whereas the SGLT-2 inhibitor-metformin group showed a 3.6 ± 4.22 kg reduction with a mean difference of -2.6 kg (-3.17 to -2.03 kg), $p < 0.0000$. Using these data, we calculated a sample size using a mean difference formula. With a power of 80% (alpha level of 0.05) in a two-sided T-test, the sample size required is 90 patients: 45 patients in the M group and 45 patients in the D/M group. The final sample size required is 108 patients: 54 patients in metformin and 54 patients in the dapagliflozin group, allowing for a 20% dropout rate.

Variable definition

Variable name	Variable Type	Scale	Conceptual definition	Operational definition	Units
INDEPENDENT VARIABLES					

Type of treatment	Qualitative, dichotomic	Nominal	Metformin is a biguanide with effect in cyclic AMP kinase that diminishes insulin resistance. Diabetes treatment guidelines consider it as the first line therapy. Dapagliflozin is an SGLT2 inhibitor that induces glycosuria and has been approved for monotherapy in patients with metformin intolerance and also as a second or third line therapy for diabetes.	Use of metformin 2 grams per day or use of metformin 2 grams per day in combination with 10 mg of dapagliflozin.	0 = metformin, 1 = metformin/dapagliflozin
-------------------	-------------------------	---------	--	--	---

DEMOGRAPHIC VARIABLES

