Age	Quantitative, continuous	Ratio	Time elapsed from birth to	Time elapsed from birth to the baseline registry of the patient.	years
-----	--------------------------	-------	----------------------------	--	-------

			the current date.		
Gender	Qualitative, dichotomic	Nominal	Taxon that gathers members of the same species.	Gender assigned in the registry documents.	0 = female 1 = male
Height	Quantitative, continuous	Ratio	Length of a human body when measured in a standing position from the top of head to the floor.	Height registered in the baseline documents using the same stadiometer in all patients during the first evaluation.	meters (m)
Body mass index (BMI)	Quantitative continuous	Ratio	Measurement that associates height and size in the same individual and classifies them as underweight, normal, overweight or obese.	Ratio between weight in kilograms (kg) divided by the square of the height in meters. Calculation is performed in every clinical evaluation during the protocol.	kg/m²
DEPENDENT VARIABLES					
Weight	Quantitative continuous	Ratio	The force that gravitation exerts upon a body.	Total amount of kilograms registered in the same person using the same calibrated scale at baseline and months 3, 6 and 12.	kilograms (kg)

Waist circumference (WC)	Quantitative continuous	Ratio	Measurement of the body circumference measured at the minimum circumference between the iliac crest and the rib cage.	Perimeter registered in the documents using the same flexible tape at baseline and months 3, 6 and 12.	centimeters (cm)
Fasting Glucose	Quantitative continuous	Ratio	Glucose concentration in the blood serum after an 8 hour fast.	Blood glucose reported at baseline, months 3,6 and 12.	mg/dl
Fasting Insulin	Quantitative continuous	Ratio	Insulin concentration in the patients serum determined by radioimmunoassay after an 8 hour fast.	Blood insulin reported at baseline and months 3,6 and 12.	mU/L
HOMA-IR	Quantitative continuous	Ratio	The homeostatic model assessment (HOMA) is a method used to quantify insulin resistance and beta-	HOMA = [glucose (mg/dl)/18 *insulin (mU/L)]/22.5 at baseline and months 3,6 and 12.	Dimensionless

			cell function.		

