Interleukine 10 (IL-10)	Quantitative continuous	Ratio	Anti-inflammatory cytokine related to the development of atherosclerosis	Concentration determined using the method ELISA.	pg/ml
Ghrelin	Quantitative continuous	Ratio	Hormone secreted in the gastric fundus that induces appetite.	Concentration determined using the method ELISA.	pg/ml

Glucagon	Quantitative continuous	Ratio	Hormone produced by pancreatic alpha cells that counteracts the effects of insulin.	Concentration determined using the method ELISA.	ng/ml
----------	-------------------------	-------	---	--	-------

Statistical analysis: Quantitative variables were described using measures of central tendency and dispersion according to the data distributions. Qualitative variables were described using frequencies or percentages. The Shapiro-Wilk test was used to establish normality in the distribution of quantitative variables. Because information on the different quantitative variables was available up to different time periods, a mixed model analysis was performed using the restricted maximum likelihood (REML) method, as well as a mixed model considering the fixed effects of assigned treatment, sex, and prediabetes or diabetes status, and the random effects of variability in weight loss over time. Comparisons between groups were analyzed using Sidak's post-hoc test. Pearson's chi-square test or Fisher's exact test were used to evaluate the association between qualitative variables. Statistical significance was defined as a $p < 0.05$. Data analysis was performed using SPSS version 17.0 and STATA version 11.0.

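### The hypothesis is a 5-percentage-point difference in weight loss, the trial is sized on 2.5 kg, and the analysis names neither scale

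*Combined protocol and SAP*

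**What the plan says.** - **Section 5, Hypothesis.** "Dapagliflozin in combination with metformin induce 10% of weight lost and 5% of decrease in waist circumference", "in comparison with the 5% of weight lost and lack of effect in the rest of parameters" on metformin alone. For weight this is 10% against 5%, a difference of 5 percentage points.
- **Section 6, primary objective.** Whether the combination "is more effective than monotherapy with metformin for weight loss". No scale is given.
- **Section 8, Sample size.** The inputs are changes in kilograms at one year from a meta-analysis in patients with mean BMI 31.7: "the placebo-metformin control group showed a reduction in body weight of 1.1 ± 3.39 kg", and "the SGLT-2 inhibitor-metformin group showed a 3.6 ± 4.22 kg reduction with a mean difference of -2.6 kg". The result is 45 per arm for 80% power at two-sided 0.05. Entry to this trial requires BMI of at least 40.
- **Section 8, Statistical analysis.** A REML mixed model with fixed effects of treatment, sex and prediabetes or diabetes status, and "the random effects of variability in weight loss over time". The response could be weight, kg change or percent change. Baseline weight is not listed as a covariate.

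Two other places are context only. Secondary objective iii counts patients in whom combined treatment "achieves a decrease in total weight of 5%, 10% and 15" percent. The variable table defines weight as "Total amount of kilograms registered in the same person using the same calibrated scale at baseline and months 3, 6 and 12", which is a recording unit.

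**The concern.** The hypothesis and the sample size should describe the same effect, because the power statement is a promise about the hypothesis. Here one is a difference in percent and the other a difference in kilograms from a much lighter population, and nothing connects them. A reader cannot tell what power the trial has for the effect it claims to expect.

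The analysis section does not settle which quantity is tested. The trial is open-label, so investigators can see how results are developing by arm. With two defensible scales and no named primary one, the scale can be chosen once the results are known.

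**Working it through.** **1. Reproduce the planned size.** Formula: n per arm = 2(1.960 + 0.842)² × (SD/difference)².

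With a difference of 3.6 − 1.1 = 2.5 kg and SD 4.22 kg (the larger of the two quoted SDs), n = 2 × 7.849 × (4.22/2.5)² = 44.7, so 45. This matches the plan. Power with 45 per arm is 80.2% by the normal approximation and 79.4% by the exact t-test. The size is therefore a kilogram calculation.

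**2. Compare the two planning effects.** The documents give no weight distribution for this population. Assume heights of 1.50 to 1.80 m and BMI of 40 to 50. Weight = BMI × height² then runs from 40 × 1.50² = 90 kg to 50 × 1.80² = 162 kg.
- 5% of 90 kg is 4.5 kg; 5% of 162 kg is 8.1 kg.
- 2.5/90 = 2.8%; 2.5/162 = 1.5%.
- The hypothesised difference is 4.5/2.5 = 1.8 to 8.1/2.5 = 3.2 times the powered one.

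Converting units does not close this gap. At 115.2 kg (BMI 45, height 1.60 m), 2.5 kg and 4.22 kg become 2.17% and 3.66%. Their ratio is unchanged, so the formula returns 45 again, still for about 2 points and not 5.

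**3. Power for the stated hypothesis.** Difference 5 points, 45 per arm, two-sided 0.05. The SD of percent change is an assumption.

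| SD of percent change | n per arm for 80% (normal) | Power with 45, normal | Power with 45, exact t |
|---|---|---|---|
| 5 | 16 | 99.7% | 99.7% |
| 6 | 23 | 97.7% | 97.4% |
| 7 | 31 | 92.3% | 91.8% |
| 8 | 41 | 84.2% | 83.5% |
| 8.4 | 45 | 80.6% | 79.7% |
| 9 | 51 | 75.0% | 74.1% |
| 10 | 63 | 66.0% | 65.0% |

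The plan delivers about 80% power for its hypothesis only if that SD is about 8.4 points or less.

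**4. Effect of the unit alone.** Simulation: 45 per arm, 20,000 trials per setting, t-test on change, kg loss = percent loss × baseline weight. Baseline weight was assumed to be 115 ± 20 kg or 125 ± 25 kg. Truth was 5% against 10%.
- SD 5: percent test 99.7%, kg test 99.3 to 99.5%.
- SD 8: percent test 83.4 to 83.6%, kg test 80.9 to 81.7%.
- SD 10: percent test 64.7 to 65.3%, kg test 63.0 to 63.4%.

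The gap is 0 to 3 points. With the sample-size inputs as truth (1.1 against 3.6 kg, SD 4.22 kg), the order reverses: kg 79.1 to 79.3%, percent 77.3 to 77.8%.

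**5. Cost of leaving the choice open.** Same simulation with no treatment effect and 5% mean loss in both arms, SD 3.4 to 8. Each test alone has about 5% type I error. Declaring success if either is significant gives 5.7 to 6.5%. Values above 7% arise only if both arms lose more than the 5% hypothesised for control.

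**The case against.** The strongest reply is that this is a wording gap with little numerical consequence. Percent change can only be computed from recorded kilograms, so the variable table conflicts with nothing. Objective iii is a separate secondary endpoint, worded for the combined arm. Both points stand.

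A reader might infer that the choice of scale gives materially different power and different conclusions, or that a kg test loses a great deal. The documents do not support this. They give no SD for percent change, and under the hypothesised 5% against 10% the unit costs 0 to 3 power points. Large losses appear only if the control arm is assumed to lose 10%, whereas the hypothesis puts it at 5% and the sample size at 1.1 kg. Even for an effect proportional to body weight, adding baseline weight as a covariate brings kg power back to about 77 to 78% where the percent test has about 80%. The t-test is also the sizing tool here, not the planned mixed model.

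Nor is percent intrinsically the better scale: with the plan's kg inputs as truth it is slightly weaker. Either scale would be acceptable if named in advance. Percent is preferred because the hypothesis is written in it.

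None of this answers the mismatch between the 5-point hypothesis and the 2.5 kg planning difference, or the missing response scale.

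**Conclusion.** The point holds as a mismatch of planning effect plus an unstated primary scale. The 80% power applies to 2.5 kg with SD 4.22 kg, not to 10% against 5%. Power for the hypothesis is not established: about 99.7% at SD 5, 80% at 8.4 and 65% at 10. It would be wrong to read this as showing that the trial is underpowered, because the hypothesised effect is 1.8 to 3.2 times the powered one and the relevant SD is not given. The direction of the error is unknown.

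The open scale is a smaller matter in numbers, a type I error of about 6 to 7% instead of 5%, but it bears on the primary result of an open-label trial. The conversions rest on assumed weights of 90 to 162 kg, the power figures on assumed SDs, and the simulation on assumed baseline distributions. The conflict between the hypothesis and the sample size rests on the text alone. It should be corrected, but it does not invalidate the design.

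**What to change.** - **Statistical analysis:** name percent change from baseline body weight as the single primary response in the mixed model, add baseline weight as a covariate, and label kg change as supportive.
- **Sample size:** restate the planning difference and SD as percent change, giving the body weight assumed for the conversion. Then either reconcile that difference with the 5 points in the hypothesis, or say plainly that the trial is powered for a smaller effect than hypothesised. Converting 2.5 kg and 4.22 kg to percent is not enough. Show power over a range of SDs.
- **Primary objective:** state the same scale.

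The cost is wording and one recalculation; no new data or visits are needed. The sample-size paragraph must carry an explicit body-weight assumption. If the analysis has already been run, report both scales and say when the primary one was chosen.

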6. OBJECTIVES

- a. **Primary objective:** To determine if combined treatment with dapagliflozin and metformin is more effective than monotherapy with metformin for weight loss and assess its effects on waist circumference, triglycerides, blood pressure and inflammatory cytokines in patients with prediabetes and diabetes with obesity class III.
- b. **Secondary objectives:**
 - i. To determine efficacy of metformin monotherapy for weight loss and decrease on waist circumference, triglycerides and blood pressure in patients with prediabetes and diabetes with obesity class III.
 - ii. To compare efficacy of metformin monotherapy and combined treatment with metformin and dapagliflozin.
 - iii. To determine the percentage of patients that with combined treatment achieves a decrease in total weight of 5%, 10% and 15% and the percentage of patients that achieve a decrease in 10% of excess weight.
 - iv. To evaluate if combined treatment allows a decrease in number of drugs needed for comorbidities' control.
 - v. To evaluate prevalence of adverse effects commonly associated with dapagliflozin use (urinary and genital tract infections, hydroelectrolytic alterations) in patients with obesity class III.
 - vi. To determine serum concentration of adiponectin, resistin, IL-6, IL-10 and TNF- α before and after treatments, and compare it between groups.
 - viii. To determine serum concentration of insulin, glucagon and ghrelin before and after treatments, and compare it between groups.

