Santo et al. in 2014 conducted a prospective study for evaluating possible benefits related to pre-surgical weight decrease in patients with super-obesity. In this study, 20 patients had in-hospital strict dietary control with diets between 600 and 1500 kcal plus aerobic physical activity (in those allowed to do it). Patients obtained a reduction of 19.7% of initial weight, with decrease of BMI

from 67 kg/m² to 55 kg/m² over a 24-weeks period. In this group, they observed a lower incidence of complications and decreased time of hospitalization [11].

Prevalence of comorbidities in the Obesity Clinic

The Obesity Clinic evaluates a population of approximately 400 patients, 150 patients have undergone bariatric surgery, 250 patients are pending of approval for such proceedings and up to 10 new patients per month are assessed for determine its possible admission to the clinic.

Sanchez-Ruiz et al. previously performed a retrospective study with a sample of 109 patients from the Obesity Clinic who underwent bariatric surgery between January 2009 and December 2011 (in press). In this study, the mean age was 45.3 ± 10.1 years, 70% were female, 85% reported attachment to diet (up to 80%), 31% performed physical activity (defined as at least 30 minutes of daily walking), 21% were smokers, 74% had a family history of obesity and 67% reported overweight or obesity since childhood. In this study, we observed that 46% of patients had prediabetes (defined by the American Diabetes Association, [ADA] as a plasmatic fasting level greater than 100 mg/dl and less than 126 mg/dl or a 2-h plasma glucose level measured after a 75-g oral glucose load, greater than 140 mg/dl and less than 200 mg/dl) or T2D (defined as fasting glucose greater than 126 mg/dl or a glucose level post-load greater than 200 mg/dl) [12], 66% had HTN and 33% had dyslipidemia (hypertriglyceridemia, hypoalphalipoproteinemia, or both). At this clinic, patients with prediabetes or T2D are usually treated with metformin 2 g/day or Neutral Protamine Hagedorn insulin (NPH) with calculated doses of 0.5 to 1 U/kg of weight when necessary and are evaluated every three months for treatment adjustment depending on their glycated hemoglobin as stipulated by ADA guidelines [12].

Pharmacological treatment of obesity

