8. PATIENTS, MATERIAL AND METHODS

Type of study: Phase II/III, controlled, randomized, open clinical trial.

By study groups: two parallel groups' design.

By maneuvering: experimental

By measurements in the population: longitudinal

By temporality: prospective

By the nature of the study: clinical

By purpose: Therapeutic

Study Population

- Patients with obesity class III from the "Obesity Clinic" in preparation for bariatric surgery.
- Study period: December 2016 to October 2018
- Place of study: Mexico City, Mexico
- Time of clinical assessment of each patient: one year

Workplan

- 1) A convenience sampling will be done for patients diagnosed with diabetes or prediabetes according to ADA criteria [12] (Appendix 1), who come to Obesity Clinic in the indicated period and that meet the selection criteria. Since the first assessment, patients are informed that they would become candidate for bariatric surgery (bypass or gastric sleeve, depending on surgeons' criteria) once they achieve a weight reduction of 10%.
- 2) Due patients achieve weight loss needed for the surgical procedure at different times of follow-up (3, 6 or 12 months), clinical, biochemical, and initial and final determinations of inflammatory cytokines and hormones, will be collected until the previous valuation before surgery. Data will be collected even if the patients require treatment with sulfonylureas or insulin (adverse event grade 3).
- 3) Prevalence of comorbidities at baseline and the type and dose of drugs used for treatment will be recorded (Appendix 2. Data Collection Sheet). Treating physicians based on the clinical response of patients, will decide the dose and number of drugs and will record changes in the corresponding data sheet.

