- 4) Patients will be randomized by a random numbers system generated with a computational software and will be assigned to a group: 1) metformin (2 g/day) or 2) metformin (2 g/day) and dapagliflozin 10 mg. All patients will receive dietary treatment and follow-up during the study by Nutrition service. Dietary treatment is individualized, as it is based on the initial weight of the patient and their eating habits at the time of valuation. It is expected that dietary treatment does not influence the results because all patients will undergo diet and those with little attachment (defined as failure to comply with at least 80% of the prescribed diet) are discharged of the surgical protocol. The Nutrition service calculates the percentage of adherence to diet.
- 5) Once assigned to the corresponding group, patients will receive an identification code that will be retained throughout the study. One of the researchers not directly involved in patient care, will assign tablets needed for daily intake for a month and then the number of tablets required for 3 months in a sealed envelope.
- 6) A run-in period will be used to assess tolerance to treatments. This period will be for a month. At this time patients will be advised of a possible increase on urea and will be instructed in the relevance of increasing fluid intake.
- 7) The anthropometrical and biochemical variables will be recorded at baseline and at 1, 3, 6 and 12 months (Appendix 2. Data Collection Sheet). A clinical nutritionist accredited as Level 1 Anthropometrist by the International Society for the Advancement of Kinanthropometry (ISAK) will assess the weight on a scale with a

maximum capacity of 300 kg and precision of 100 g; height using an stadiometer, and waist circumference using a fiberglass tape, according to the manual of procedures for nutrition projects of the Centro de Investigación en Nutrición y Salud de Instituto Nacional de Salud Pública [86], and also in accordance with the procedures manual for the assessment of clinical and anthropometrical measurements in the adult and elderly of the Ministry of Health [87] (Appendix 3. Clinical and anthropometric measurements).

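### Secondary objective i asks for the efficacy of metformin, but both arms receive metformin and diet, so the group 1 change from baseline can only be described, not attributed to metformin

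*Combined protocol and SAP*

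**What the plan says.** Section 6 (Objectives) lists as secondary objective i: "To determine efficacy of metformin monotherapy for weight loss and decrease on waist circumference, triglycerides and blood pressure". Objective ii, a separate item, is the comparison of metformin with the combination.

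Section 5 (Hypothesis) expects in the control arm "5% of weight lost and lack of effect in the rest of parameters in patients treated with metformin monotherapy".

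Section 8, Workplan item 4, assigns patients to "metformin (2 g/day) or 2) metformin (2 g/day) and dapagliflozin 10 mg", and adds: "All patients will receive dietary treatment and follow-up during the study by Nutrition service". It then argues: "It is expected that dietary treatment does not influence the results because all patients will undergo diet". Under Workplan item 3, treating physicians "will decide the dose and number of drugs and will record changes in the corresponding data sheet".

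Section 7 (Background) says of this clinic that "patients with prediabetes or T2D are usually treated with metformin 2 g/day". The exclusion criteria name insulin, sulfonylureas and drugs for weight control, but not metformin, and the Abstract admits patients with previously diagnosed diabetes or prediabetes.

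The statistical analysis paragraph plans a mixed model with assigned treatment, sex and glycaemic status as fixed effects, Sidak comparisons between groups, and significance at p < 0.05. It gives no equivalence margin and no equivalence test.

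**The concern.** Objective i stands apart from the between-arm objective, so it can only be answered from the change over time in group 1. An efficacy claim needs a comparison with patients who do not get metformin, and the trial has none. If the objective is reported as worded, weight lost through diet, or lipid and blood pressure changes caused by adjusted co-medication, would be credited to metformin.

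The hypothesis raises a related point. It expects metformin to leave the other parameters unchanged, but the plan has no means of showing that. It also sits awkwardly beside objective i, which looks for decreases in three of those same parameters (waist, triglycerides, blood pressure).

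**Working it through.** **1. What the randomisation identifies.**

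- Group 1: metformin + diet.
- Group 2: metformin + diet + dapagliflozin.
- Group 2 minus group 1: dapagliflozin added to metformin and diet.

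Metformin and diet cancel in the difference, so the Workplan's argument about diet is sound for that contrast. They do not cancel in the change from baseline within group 1.

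**2. What the group 1 change contains, from the plan's own text.**

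- Individualised diet; patients complying with less than 80% of it leave the surgical protocol (Workplan item 4).
- Motivation: patients are told that a 10% weight reduction makes them candidates for surgery (item 1).
- Follow-up that ends before surgery, at 3, 6 or 12 months according to the weight lost (item 2).
- Changes in dose and number of co-medications (item 3), which bear on triglycerides and blood pressure.
- Possibly no start of metformin at all, for patients already taking it as usual care.

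The cited literature illustrates the hazard. An uncontrolled series of metformin plus hypocaloric diet reports 15.1 kg lost at 12 months in its higher-BMI group (Background). The placebo-metformin arm of the meta-analysis used for the sample size lost 1.1 kg at one year. An in-hospital diet and activity programme alone gave a 19.7% loss over 24 weeks (Background). The populations differ, so this only illustrates how little an uncontrolled change says about metformin.

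**3. What the sample size covers.** Inputs from Sample size: control change 1.1 kg (SD 3.39), combination change 3.6 kg (SD 4.22), two-sided alpha 0.05, power 80%. Using the difference 3.6 − 1.1 = 2.5 kg and SD 4.22:

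n per arm = 2 × (1.960 + 0.842)² × (4.22 / 2.5)² = 44.7, rounded up to 45.

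This reproduces the plan's 45 per arm. It sizes the between-arm difference in weight and nothing else.

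**4. Precision within group 1 at n = 45.**

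- 95% CI half-width = t(0.975; 44) / √45 × SD = 2.015 / 6.708 × SD = 0.30 SD. For weight at SD 3.39 kg this is ±1.02 kg.
- Power to detect the plan's own 1.1 kg control change: noncentrality 1.1 / 3.39 × 6.708 = 2.18, so about 57%.

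Even a significant result would remain the joint effect listed in step 2.

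**5. Risk in reading non-significance as no effect.** Assume a true 5% fall, the size hypothesised for the combination, and a two-sided one-sample t-test with n = 45. This test is an illustration; the plan does not name it. Noncentrality = 5 / SD × 6.708. The documents give no SD of percentage change, so a range is shown.

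| Assumed SD (points) | Noncentrality | Chance of p > 0.05 |
|---|---|---|
| 10 | 3.35 | 9% |
| 15 | 2.24 | 41% |
| 20 | 1.68 | 63% |
| 30 | 1.12 | 81% |

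**6. Waist circumference.** The Background cites a 24-week placebo-controlled dapagliflozin trial in 182 patients with a waist difference of 1.52 cm (2.74 to 0.31). Reading the interval as 95% and assuming 91 per arm:

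- SE = (2.74 − 0.31) / (2 × 1.96) = 0.62 cm.
- SD = 0.62 / √(2/91) = about 4.2 cm.
- At an assumed mean waist of 100 to 140 cm, the SD is about 3 to 4%.

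The noncentrality is then at least 8, and a true 5% fall would be missed in well under 0.1% of cases.

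**The case against.** The strongest reply is that the trial is plainly comparative. The research question, the primary objective and objective ii all concern the difference between arms. The phrase "lack of effect in the rest of parameters in patients treated with metformin monotherapy" is the expected control value inside a comparative hypothesis. The analysis paragraph names no within-arm test of metformin and no rule for accepting a null result. This stands. A reader might infer that the trial will present a non-significant change as proof that metformin does nothing, but no text says so. A reader might also infer that such a null result is nearly guaranteed by the sample size. The documents do not support that either: it would need large SDs for every parameter, and the waist data point the other way.

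A second reply is that prior treatment is already captured. This also stands. Workplan item 3 records the type and dose of drugs at baseline, and Appendix 2 has a drug column beside the prediabetes and diabetes rows. Only a tabulation by arm is missing.

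A third reply is that diet is openly common to all patients, so nobody would be misled. This helps only between arms. Objective i is written as a separate efficacy question, and none of these replies supplies a metformin-free comparator.

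**Conclusion.** The point holds for objective i: the change in group 1 can be described but not attributed to metformin. This follows from the design and does not depend on any assumed SD or sample size.

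For the hypothesis, the point is a caution. With no margin and no equivalence test, a non-significant within-arm change must not be reported as absence of effect. The chance of missing a true 5% fall with 45 patients runs from about 9% to 81% over assumed SDs of 10 to 30 points. It therefore concerns highly variable measures; triglycerides and cytokines may be among them, but the documents do not give their SDs. It does not concern waist circumference. The primary comparison of the combination with metformin is unaffected.

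**What to change.** - Restate objective i as the change from baseline in group 1 under metformin plus diet, reported with a 95% CI and without attributing it to metformin.
- Word the hypothesis for waist, triglycerides, blood pressure and cytokines as between-arm differences. This also removes the mismatch with objective i. If absence of a change under metformin plus diet is really to be claimed, a margin and an equivalence test must be pre-specified.
- Tabulate prior metformin use by arm from the drug data already recorded at baseline.

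The cost is the wording of one objective and the hypothesis, plus one table. No extra patients, visits or assays are needed. The downside is giving up a claim of metformin efficacy, which the design cannot support.
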